10.5 Immunogenicity Analyses

Immunologic analyses will be conducted using the ITT and PP Populations, with primary conclusions drawn from the PP Population. The primary variable of interest for assessment of immune response to the RSV F vaccine will be anti-F IgG EU and PCA concentration, and testing by these methodologies will have the highest priority. The secondary variables will be RSV/A and B MN titers, which will be determined on all blood samples, but with priority testing assigned to samples collected at the following time-points: at delivery for the maternal subject, and at delivery, D+14, D+35, D+60, D+90, D+120, and D+180 for the infant subject.

The following immunogenicity outcome measures and their 95% CI will be summarized by treatment group. Immunogenicity analyses will be descriptive and include tabulations by treatment group.

Maternal Subjects:

- 1) GMEU or GMC, GMFR, proportion of subjects with ≥ 2 -fold and ≥ 4 -fold increases in EU/concentration from baseline (2- and 4-fold seroconversion rates [SCR]); and SRR of anti-RSV F IgG and PCA at baseline, post-immunization on Day 14, at delivery, and postpartum on Days 35 and 180.

- 2) GMT, GMFR, proportion of subjects with \geq 2-fold and \geq 4-fold increases in titer from baseline (2- and 4-fold seroconversion rates {SCR}); and SRR of RSV/A and B MN titers at baseline and delivery.
- 3) GMFR Transplacental Transfer Proportion, the anti-RSV F IgG GMEU, PCA GMC, and RSV/A and B MN GMT of the within-maternal-infant pair ratios for cord blood over maternal serum (MS) at delivery (GMFR_{Cord/MS}).

Infant Subjects:

- 1) GMEU, GMC, or GMT; and SRR of anti-RSV F IgG, PCA, and RSV/A and B MN antibodies in cord blood and on D+14, D+35, D+60, D+90, D+120, and D+180.
- 2) GMFR of anti-RSV F IgG GMEU, PCA GMC, and RSV/A and B MN GMT within-subject ratios after delivery (D) on D+14, D+35, D+60, D+90, D+120, and D+180 over cord blood value at delivery (GMFR_{AD/Cord}).
- 3) Exploratory modeling of anti-RSV F antibody decay in infants using first order models and infant data.

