4.1.2. Secondary Objectives

The secondary objectives of this study are:

- To determine the efficacy of maternal immunization with the RSV F vaccine in reducing the incidence in infants of:
 - RSV LRTI with EITHER severe hypoxemia (SpO_2 < 92% at sea level or < 87% at altitudes > 1800 meters) or the documented use of oxygen by high flow nasal cannula OR a requirement for continuous positive airway pressure (CPAP) or bilevel positive airway pressure (BiPAP) OR Bubble CPAP OR bag-mask ventilation OR intubation with subsequent mechanical (or manual) ventilation OR extracorporeal membrane oxygenation (ECMO), through the first 90 days of life in infants of maternal RSV F vaccinees as compared to placebo recipients. In the event that efficacy is shown through the first 90 days of life, a hierarchical sequence of hypothesis tests will be carried out to examine efficacy at 120, 150, and 180 days of life.
 - RSV LRTI leading to hospitalization through the first 90 days of life in infants of maternal RSV F vaccinees as compared to placebo recipients. In the event that efficacy is shown through the first 90 days of life, a hierarchical sequence of hypothesis tests will be carried out to examine efficacy through 120, 150, and 180 days of life.

The two secondary efficacy objectives will be evaluated in term infants (≥ 37 weeks gestational age at delivery) born to maternal subjects who received a study injection ≥ 2 weeks (14 days) prior to delivery. Infants with multiple RSV episodes meeting a given criterion will be counted

only once, using data from the first episode. Success under the secondary efficacy hypotheses will be achieved by demonstration of a lower bound of a two-sided 95% confidence interval for the estimate of vaccine efficacy which exceeds 0%.

- To describe the immunologic responses to the RSV F vaccine in healthy maternal subjects, in the third trimester of pregnancies deemed to be at low risk of obstetrical complications, through delivery and six months thereafter.
- To describe the transplacental transfer of maternal antibodies specific for RSV and its F protein based on the ratio of levels in maternal and cord blood at delivery.
- To estimate the rate of decay of RSV and F protein-specific antibodies in infants through the first six months of life.
- To develop an immune correlate of risk of the RSV LRTI syndromes in infants based on anti-F protein antibody and/or palivizumab-competitive antibody levels measured in the infant and/or cord blood.

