11.1. Analysis of the Secondary Objectives of Immunogenicity

The principal variables of interest for assessment of immune response to the RSV F vaccine will be anti-F IgG EU and PCA concentrations that will be determined at all prospectively defined time-points as stated below. Additional immunogenicity variables will be RSV/A and B MN titers, which will be measured at the baseline and delivery visits for maternal subjects and at the delivery and D+14, D+35, D+60, D+90, D+120, and D+180 visits for infant subjects. For the analysis of paired immunogenicity measures, geometric mean of fold rise in post-vaccination measures compared to baseline (pre-vaccination) in maternal subjects (GMFR) and geometric mean ratio (GMR) of paired samples over time within a maternal subject, an infant subject, or a maternal and infant subject pair (GMR) will be summarized. GMC, GMEU, GMT, and GMFR/GMR will be calculated as the antilog of the mean and 95% CI of \log_{10} -transformed values. The values reported as below the LLOQ of the assay will be set to half of LLOQ. In addition, seroconversion rates (SCR) based on ≥ 2 - and ≥ 4 -fold rise thresholds and seroresponse rates (SRR) will be calculated as defined below.

The following immunogenicity outcome measures and their 95% CI will be summarized by treatment group.

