11.1.4. Infants Antibody Decay Modeling

To estimate the decay of antibody levels in per protocol infants (PP-IMM-I) that result from RSV F protein vaccine immunization in pregnant women, the log10 transformed antibody

levels will be used as the independent variable and the actual age of infant subjects in days at the time of sample collection as the exploratory variable in the regression analysis. The estimated slope will be used to estimate the half-life as $\log_{10}(2)/\text{slope}$ with the corresponding 2-sided 95% confidence interval. All observed values, except for the measures reported as < LLOQ, for each time-point and infant cohort (Phlebotomy Cohort 1, Cohort 2, and Cohort 3) will be pooled to assess the persistence of anti-F IgG antibody, PCA, and/or MN levels over time. Since values reported as < LLOQ do not provide the exact time when the values crossed the LLOQ, they will be excluded from the half-life estimation. All measurements from subjects with at least two \geq LLOQ measures will be included in the analysis. A conventional first order antibody decay model will be used for analysis. A second order or other, more complex, antibody decay model may be further developed to explain the rate of decay of antibody levels in the infants in the study, albeit the dataset may not be sufficiently rich to support more complex models.

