16. DATA HANDLING CONVENTIONS

All statistical analyses will be 2-tailed and assessed at the 5% significance level.

All output will be incorporated into Microsoft Word (including rtf format) or Excel files, or Adobe Acrobat PDF files, sorted and labeled according to the International Conference on Harmonization (ICH) recommendations, and formatted to the appropriate page size(s).

Tabulations will be produced for appropriate demographic, baseline, and safety parameters. For categorical variables, summary tabulations of the number and percentage of subjects within each category (with a category for missing data) of the parameter will be presented. For continuous variables, the number of subjects, mean, median, standard deviation (SD), minimum, and maximum values will be presented.

For all analyses, a two-sided p-value of < 0.05 (one-sided p-value < 0.025 where appropriate) will be considered statistically significant except for the primary efficacy endpoint, medically significant RSV LRTI through 90 day that will be evaluated using a one-sided p value of 0.0124

All references to analysis of GMEU/GMC/ GMT will be interpreted as analysis of the log (base 10) of EU or concentration values or of the reciprocal titers (e.g., the reciprocal titer of 1:160 is the number 160). Values recorded as below the lower limit of quantitation (LLOQ) of the assay for PCA and anti-F IgG will be set to half LLOQ for the purposes of GMEU/GMC, and GMFR analyses. For MN assays, titers will be reported in International Unit (IU) with the LLOQs of 13 for RSV/A and 8 for RSV/B. Titers below the LLOQs will also be set to half LLOQ, 6.5 IU for RSV/A and 4 IU for RSV/B.

For all data analyses and summary tabulations, categories for analysis and presentation will consist of the RSV F vaccine treatment groups. All descriptive statistical analyses will be performed using SAS statistical software Version 9.3 or higher in a Windows environment, unless otherwise noted. Medical history and AEs will be coded using the MedDRA Version 16.1.

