16.4. Multiple Comparisons/Multiplicity

Analysis of the primary efficacy endpoint, medically-significant RSV LRTI in infant subjects, will be performed following a hierarchical closed procedure to control for the overall Type I error rate at 1-sided 0.025. A demonstration of vaccine efficacy through the first 90 days at a Type I error rate of 0.0124 (i.e., lower bound of two-sided 97.52% CI above the pre-specified threshold) will be required prior to testing of subsequent time-points, through 120, 150, and 180 days at Type I error rate of 0.025 (i.e., lower bound of two-sided 95% CI above the pre-specified threshold). Two sets of parallel analyses will be performed for the primary efficacy endpoint, one set for the US-FDA and the other for the ex-US global regulatory submissions (e.g., EMA and WHO) using different success criteria for the primary endpoint, H_0 : Vaccine Efficacy $<$ 30% for the US-FDA and H_0 : Vaccine Efficacy \leq 0% for the ex-US global regulatory submissions. The two sets of analyses will be the same for all other statistical approaches (i.e., methods of analysis, Type I error adjustments, and hierarchical testing approach).

Analysis of secondary and exploratory efficacy endpoints and immunogenicity endpoints will be performed without adjustment for multiple comparisons. The final interpretation of the total vaccine efficacy and the duration of protection will be based on the totality of statistical evidence including immunogenicity results and pre-specified exploratory endpoints; and the clinical importance in discussions with the regulatory agencies and scientific communities.

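### The infant decay model drops values below the LLOQ from a pooled regression with no infant term, so half-life is overstated if a material share of late values is below the LLOQ

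*SAP*

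**What the plan says.** SAP 4.1.2 lists as a secondary objective: "To estimate the rate of decay of RSV and F protein-specific antibodies in infants through the first six months of life". SAP 11.1.4 sets out the model:

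- Log10 antibody "levels will be used as the independent variable and the actual age of infant subjects in days" is the explanatory side of a first-order regression. Half-life is log10(2) divided by the slope, with a two-sided 95% CI.
- Quantifiable values from every time-point and all three phlebotomy cohorts are pooled.
- "All measurements from subjects with at least two" quantifiable values are included.
- Values below the LLOQ "do not provide the exact time when the values crossed the LLOQ, they will be excluded from the half-life estimation".

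No random effect, repeated-measures term or censored likelihood is named, and more complex decay models are optional. The change list in SAP 18.2 shows that the exclusion was deliberate. The SAP treats the same values differently for geometric means and ratios: "The values reported as below the LLOQ of the assay will be set to half of LLOQ" (SAP 11.1). SAP 16.8 describes sensitivity analyses for the primary efficacy endpoint only.

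**The concern.** The stated reason for the exclusion does not apply. The regression uses antibody level at a known age, not the time at which a titre crosses a threshold. A result below the LLOQ at a known age is an ordinary left-censored observation.

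An infant whose late value is below the LLOQ will usually still have two quantifiable earlier values, so it stays in the analysis and only its low late value disappears. Late ages then over-represent infants who started high, and the pooled line is too flat. With up to three samples per infant and no infant term, nothing in the model corrects this.

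The error favours the vaccine, because it suggests longer persistence. SAP 16.4 says that interpretation of "the duration of protection will be based on the totality of statistical evidence including immunogenicity results", so the half-life can feed that judgement.

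**Working it through.** **Inputs from the documents.** Sampling ages are cord blood plus Days 14 and 90 (Cohort 1), 35 and 120 (Cohort 2), or 60 and 180 (Cohort 3) (protocol 7.2). SAP 13 estimates 2,786 per-protocol vaccine-group infants. That is the efficacy estimate, whereas the decay model uses the infant immunogenicity set, but the number of infants does not drive the bias. For microneutralization (MN), SAP 16 says: "For MN assays, titers will be reported in International Unit (IU) with the LLOQs of 13 for RSV/A and 8 for RSV/B". The documents state no half-life, antibody SD, cord level, share below the LLOQ, or LLOQ for anti-F IgG or PCA, so there is no planned figure to reproduce.

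**Assumptions.** True half-life 30, 40 or 50 days; between-infant SD 0.25–0.45 log10; residual SD 0.12–0.20 log10; log-linear decay.

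**1. Formula and variable roles.** With log10 C(t) = a + b·t and half-life H, b = −log10(2)/H. For H = 40, b = −0.30103/40 = −0.00753 per day, and log10(2)/b = −40 days: the sign is wrong. If antibody really were the independent variable, the noise-free slope would be 1/b = −132.9 days per log10. Then log10(2)/slope = −0.0023 per day, which is not a half-life.

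**2. Size of the bias.** The SAP rule was simulated (120 datasets of 2,784 infants in each of 108 scenarios, with protocol visit windows) and fitted as ordinary pooled regression:

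| Day-180 values below LLOQ | Half-life overstated by |
|---|---|
| 0% | none |
| 1% | 0.4–1.0% |
| 5% | 1.2–4.0% |
| 10% | 2.1–7.4% |
| 15% | 2.9–10.7% |
| 30% | 4.8–20.9% |

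At a true 40 days, the overstatement is 1.7–8.1% for 5–15% (0.7–3.2 days) and 6.8–15.6% for 30% (2.7–6.2 days). A separate run with 60,000 infants per scenario (true 40 days, between-infant SD 0.40) gave 40.3 days at 2%, 41.2 at 6%, 43.0 at 17%, 45.9 at 37% and 55.9 at about 80%.

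Day 180 supplies one of nine cohort-by-age cells, so a 10% share there is about 10%/9 = 1.1% of all infant samples, or 1.2–1.5% once a few earlier values are added. A low overall rate would not reveal the problem.

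**3. What drives it.** A within-infant slope on the same truncated data was only 0.1–2.1% too long at 5–15% and 0.5–3.9% at 30%. Most of the bias therefore comes from combining exclusion with pooling.

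**4. Confidence interval.** With nothing below the LLOQ, the pooled standard error was 1.3–1.8 times too large, so the interval is too wide, not too narrow. With values excluded, it is centred on a biased estimate. At 37% of Day-180 values below the LLOQ and 1,500 infants, the nominal 95% interval covered the true slope in 0 of 400 runs.

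**5. When it could arise for MN.** At a 40-day half-life, titres fall 2^(180/40) = 22.6-fold by Day 180. At least 10% of Day-180 values are below the LLOQ if the cord GMT is under LLOQ × 22.6 × 10^(1.2816 × SD). For total SD 0.3–0.5 log10 that is 713–1,286 IU for RSV/A (LLOQ 13) and 439–792 IU for RSV/B (LLOQ 8).

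**6. Does the remedy work?** Left-censored random-intercept likelihood, 15–25 datasets of 600 infants, true half-life 40 days. Results are in days, at 10% and 30% of Day-180 values below the LLOQ:

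| Data | SAP rule, pooled | Censored model |
|---|---|---|
| Log-linear | 41.6, 44.5 | 39.9, 40.0 |
| Random slopes | 41.9, 44.8 | 40.0, 40.0 |
| Skewed infant effects | 41.5, 43.1 | 40.1, 39.7 |
| Bi-exponential | 40.6, 43.1 | 39.2, 39.1 |

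The bi-exponential data give 39.3–39.4 days with no censoring. Half-LLOQ substitution in the regression is not a reliable alternative: in the larger simulation it gave 39.4 to 50.7 days against a true 40.

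**The case against.** The strongest objection is that the report will contain its own check. SAP 11.1 and 11.1.1 plan within-infant ratios to cord blood through Day 180, with values below the LLOQ kept at half LLOQ and no two-value filter. In simulation with 5–30% of Day-180 values below the LLOQ, the half-life implied by the Day-180-to-cord ratio was within about 3.5% of the truth. A careful reader could therefore see the discrepancy. That stands, but the SAP does not designate the ratio as a half-life estimate or as a check on the exclusion.

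Second, the trigger is unknown. Vaccine-group levels may stay well above the LLOQ, in which case the bias is nil, and MN, the only assay with stated LLOQs, is an additional variable. This stands, and it is why the concern is conditional.

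Third, SAP 11.1.4 does not actually say ordinary least squares, and a two-value rule makes most sense for a within-infant slope, which would be nearly unbiased. That is a fair reading, but the text specifies pooling and names no infant term, so a programmer could properly fit either model.

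Fourth, no test or threshold depends on the half-life, and protocol 10.5 describes the work as "Exploratory modeling of anti-RSV F antibody decay in infants using first order models and infant data". This limits the importance of the point without making the rule sound.

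**Conclusion.** The concern holds. Exclusion and pooling are explicit, no infant term or censored likelihood is named, and the bias lengthens half-life whenever a material share of late values is below the LLOQ. The percentages rest on the assumed half-lives and SDs and on an ordinary pooled fit. The actual share below the LLOQ cannot be determined from the documents, and at about 1% of Day-180 values the effect is negligible. The two drafting errors stand whatever that share is. This is a worthwhile correction to a descriptive secondary estimate.

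**What to change.** Amend SAP 11.1.4 as follows:

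- Make log10 antibody the dependent variable and actual age in days the explanatory variable, with an infant random intercept.
- Keep values below the LLOQ as left-censored observations in the likelihood (for example, in SAS NLMIXED) and drop the two-value filter.
- Define half-life as −log10(2)/slope, with its 95% CI.
- Report the share below the LLOQ by assay and age.
- Retain the present exclusion rule as a sensitivity analysis.

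This needs revised SAP wording, a different model call and no new data. The price is somewhat more modelling work and reliance on normal random effects and log-linear decay. If a censored likelihood is unwelcome, naming an infant term alone removes most of the bias: in the larger simulation at a true 40 days, it gave 40.4 days where the pooled rule gave 45.9 (37% of Day-180 values below the LLOQ).

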11.1.5. Immune Correlate of Risk of the RSV LRTI Syndromes in Infants

Analyses will be performed to attempt to identify a correlate of risk (CoR) for the RSV LRTI syndromes in infants based on anti-F IgG and/or PCA levels measured in the infant and/or cord blood and the maternal subjects at Day 14 post-vaccination and delivery. For the purpose of this analysis, the CoR is defined as a general inverse relationship between the level of an immune response parameter before the onset of the first episode of a RSV infection and the RSV disease status. RSV immune measure(s) will be tabulated for each primary and secondary efficacy disease endpoint status for each treatment group and for the combined treatment groups. Qin et al. define a surrogate of protection (SoP) as a CoR that reliably predicts a vaccine's level of protective efficacy on the basis of differences between the vaccinated and unvaccinated groups' immunological measurement(s). Appropriate SoP validating methods as proposed in Qin et al. will be used to explore if the chosen CoR is a potential SoP [Qin 2007].

Two sets of graphs will be created for each primary and secondary efficacy disease endpoint status as screening tools to identify CoRs that are potential SoPs for further assessment.

The first set, which will comprise graphs for each endpoint and each time-point, will show cumulative distribution functions displaying the level of anti-F IgG and PCA levels for the combined treatment group and for each treatment group separately.

The second set, which will consist of receiver operating curves (ROC), will have six graphs for each endpoint, one for each marker and blood pair. If the clinicians consider the area under the ROC curve sufficiently high, the marker will be deemed a CoR. As a rule of thumb, markers with areas of 0.9 and above are considered excellent while those with areas between 0.8 and 0.9 are considered good [Pepe 2004]. Marker and blood pairs with areas under the ROC curve of at least 0.8 will be deemed candidate CoRs.

The maximum values of Youden's J Index (sensitivity + specificity -1), will be used as a first pass at selecting a cut-off value defining the level of the CoR that will be used to explore whether the CoR is a surrogate of protection. The Index assigns equal weight to sensitivity and

specificity. Different weightings may be explored if Novavax and/or external clinician experts judge equal weighting inappropriate.

Thus far, we have considered the two markers, anti-F IgG or PCA, separately. It is possible that while neither alone is an excellent CoR, some combination of the two better identifies risk, or a different immune measure (e.g., microneutralization). Exploratory analyses will be used to try to identify a function of the two markers that together constitute a CoR and/or additional immune measure(s).

12. SAFETY ANALYSES

Adverse events are defined as any unfavorable or unintended change in the physical, psychological, or biochemical condition of the subject. An AE temporally related to participation in the study will be documented whether or not considered related to the test article. This definition includes intercurrent illnesses and injuries, and exacerbations of pre-existing conditions. Stable pre-existing conditions which do not change in nature or severity during the study are not considered AEs; however, these should be collected as part of the medical history. AEs will be considered treatment emergent from the date and time of the first administration of the investigational product. All safety and reactogenicity summaries will be based on the Safety Population.

12.1. Overall Handling of Adverse Events

The principal variable for evaluation of the safety profile for the RSV F vaccine will be the number and percentage (95% CI) of maternal subjects with solicited and unsolicited adverse events (including MAEs and SAEs) recorded post-vaccination, and the number and percentage (95% CI) of infants with unsolicited AEs occurring since birth. An overall summary will present the number and percentage of solicited adverse events in maternal subjects by verbatim term and treatment group; and unsolicited adverse events by MedDRA SOC and PT, and by treatment group for all maternal and infant subjects in the Safety Population. Laboratory values and vital signs will also be summarized (percentages) by treatment group for all maternal subjects in the Safety Population.

Solicited adverse events occurring in the first 7 days after each dose of test article will be presumed to be related; and severity will be graded by specific definitions included in the protocol and subject diary. Unsolicited adverse event summaries by relationship to study vaccine will be categorized as “not related” (including “unrelated or unlikely”) or “related” (including “possible, probable, and definite”). For multiple occurrences of an adverse event in the same subject, a subject will be counted only once, using the most severe or most related occurrence for the summarization by severity or relationship to study vaccine, respectively.

Solicited adverse events will not be coded, and will be summarized by solicited term only. All unsolicited adverse events will be coded using MedDRA version 16.1.

